12.8 CONSENT PROCESS AND DOCUMENTATION

The informed consent document will be provided as a physical or electronic document to the participant or consent designee(s) as applicable for review prior to consenting. A designated study investigator* will carefully explain the procedures and tests involved in this study, and the associated risks, discomforts and benefits. In order to minimize potential coercion, as much time as is needed to review the document will be given, including an opportunity to discuss it with friends, family members and/or other advisors, and to ask questions of any designated study investigator. A signed informed consent document will be obtained prior to entry onto the study.

The initial consent process as well as re-consent, when required, may take place in person or remotely (e.g., via telephone or other NIH approved remote platforms used in compliance with policy, including HRPP Policy 303) per discretion of the designated study investigator and with the agreement of the participant/consent designee(s). Whether in person or remote, the privacy of the subject will be maintained. Consenting investigators (and participant/consent designee, when in person) will be located in a private area (e.g., clinic consult room). When consent is conducted remotely, the participant/consent designee will be informed of the private nature of the discussion and will be encouraged to relocate to a more private setting if needed.

Consent will be documented with required signatures on the physical document (which includes the printout of an electronic document sent to participant) or as described below, with a manual (non-electronic) signature on the electronic document. When required, witness signature will be obtained similarly as described for the investigator and participant.

Manual (non-electronic) signature on electronic document:

When a manual signature on an electronic document is used for the documentation of consent at the NIH Clinical Center, this study will use the following to obtain the required signatures:

- Adobe platform (which is not 21 CFR Part 11 compliant); or,
- iMedConsent platform (which is 21 CFR Part 11 compliant)

During the consent process, participants and investigators will view individual copies of the approved consent document on screens at their respective locations (if remote consent); the same screen may be used when in the same location, but is not required.

Both the investigator and the participant will sign the document using a finger, stylus or mouse.

Note: Refer to the CCR SOP PM-2, Obtaining and Documenting the Informed Consent Process for additional information (e.g., verification of participant identity when obtaining consent remotely) found at

<https://ccrod.cancer.gov/confluence/pages/viewpage.action?pageId=73203825>.

* Please note that consent for treatment must be obtained by a designated appropriately licensed study investigator (e.g., MD, NP, PA, DO). However, study investigators not falling into this category (e.g. RNs) who are designated as able to obtain consent, may do so for non-treatment procedures such as screening.

12.8.1 Consent Process for Adults Who Lack Capacity to Consent to Research Participation

For participants addressed in Section [12.3](#), an LAR will be identified consistent with Policy 403 and informed consent obtained from the LAR, as described in Section [12.8](#).

12.8.2 Request for Waiver of Consent for Screening Activities

Prior to the subject signing the consent for this study pre-screening activities listed in section [2.2.1](#) may be performed.

We request a waiver of consent for these activities as they involve only minimal risk to the subjects. A waiver will not adversely affect the rights and welfare of the subjects given that the activities are only intended to determine suitability for screening for participation in research protocols. These activities could not practicably be carried out without the waiver as central recruiting services, utilized in the NIH Clinical Center, perform pre-screening activities for multiple studies and obtaining consent for each one is beyond their resources. The subjects will be provided with additional pertinent information after participation as they will be informed whether or not they are eligible to sign a consent for additional screening.

13 REGULATORY AND OPERATIONAL CONSIDERATIONS

13.1 STUDY DISCONTINUATION AND CLOSURE

This study may be temporarily suspended or prematurely terminated if there is sufficient reasonable cause. Written notification, documenting the reason for study suspension or termination, will be provided by the suspending or terminating party to study participants, investigator, funding agency, the Investigational New Drug (IND) sponsor and regulatory authorities. If the study is prematurely terminated or suspended, the Principal Investigator (PI) will promptly inform study participants, the Institutional Review Board (IRB), and sponsor and will provide the reason(s) for the termination or suspension. Study participants will be contacted, as applicable, and be informed of changes to study visit schedule.

Circumstances that may warrant termination or suspension include, but are not limited to:

- Determination of unexpected, significant, or unacceptable risk to participants
- Demonstration of efficacy that would warrant stopping
- Insufficient compliance to protocol requirements
- Data that are not sufficiently complete and/or evaluable
- Determination that the primary endpoint has been met
- Determination of futility

Study may resume once concerns about safety, protocol compliance, and data quality are addressed, and satisfy the sponsor, IRB and as applicable, Food and Drug Administration (FDA).

13.2 QUALITY ASSURANCE AND QUALITY CONTROL

The clinical site will perform internal quality management of study conduct, data and biological specimen collection, documentation and completion. An individualized quality management plan will be developed to describe a site's quality management.

Quality control (QC) procedures will be implemented beginning with the data entry system and data QC checks that will be run on the database will be generated. Any missing data or data anomalies will be communicated to the site(s) for clarification/resolution.

Following written Standard Operating Procedures (SOPs), the monitors will verify that the clinical trial is conducted and data are generated and biological specimens are collected, documented (recorded), and reported in compliance with the protocol, International Conference on Harmonisation Good Clinical Practice (ICH GCP), and applicable regulatory requirements (e.g., Good Laboratory Practices (GLP), Good Manufacturing Practices (GMP)).

The investigational site will provide direct access to all trial related sites, source data/documents, and reports for the purpose of monitoring and auditing by the sponsor, and inspection by local and regulatory authorities.

13.3 CONFLICT OF INTEREST POLICY

The independence of this study from any actual or perceived influence, such as by the pharmaceutical industry, is critical. Therefore, any actual conflict of interest of persons who have a role in the design, conduct, analysis, publication, or any aspect of this trial will be disclosed and managed. Furthermore, persons who have a perceived conflict of interest will be required to have such conflicts managed in a way that is appropriate to their participation in the design and conduct of this trial. The study leadership in conjunction with the NCI has established policies and procedures for all study group members to disclose all conflicts of interest and will establish a mechanism for the management of all reported dualities of interest.

13.4 CONFIDENTIALITY AND PRIVACY

Participant confidentiality and privacy is strictly held in trust by the participating investigators, their staff, and the sponsor(s). This confidentiality is extended to cover testing of biological samples and genetic tests in addition to the clinical information relating to participants. Therefore, the study protocol, documentation, data, and all other information generated will be held in strict confidence. No information concerning the study or the data will be released to any unauthorized third party without prior written approval of the sponsor.

All research activities will be conducted in as private a setting as possible.

The study monitor, other authorized representatives of the sponsor, representatives of the Institutional Review Board (IRB), and/or regulatory agencies may inspect all documents and records required to be maintained by the investigator, including but not limited to, medical records (office, clinic, or hospital) and pharmacy records for the participants in this study. The clinical study site will permit access to such records.

The study participant's contact information will be securely stored at the clinical site for internal use during the study. At the end of the study, all records will continue to be kept in a secure location for as long a period as dictated by the reviewing IRB, Institutional policies, or sponsor requirements.

Study participant research data, which is for purposes of statistical analysis and scientific reporting, will be transmitted to and stored at the NCI CCR. This will not include the participant's contact or identifying information. Rather, individual participants and their research data will be identified by a unique study identification number. The study data entry and study management systems used by research staff will be secured and password protected. At the end of the study, all study databases will be de-identified and archived by the NIH.

To further protect the privacy of study participants, a Certificate of Confidentiality has been issued by the National Institutes of Health (NIH). This certificate protects identifiable research information from forced disclosure. It allows the investigator and others who have access to research records to refuse to disclose identifying information on research participation in any civil, criminal, administrative, legislative, or other proceeding, whether at the federal, state, or local level. By protecting researchers and institutions from being compelled to disclose information that would identify research participants, Certificates of Confidentiality help achieve the research objectives and promote participation in studies by helping assure confidentiality and privacy to participants.

14 PHARMACEUTICAL INFORMATION

14.1 NIVOLUMAB (IND #133973)

14.1.1 Source:

Bristol Myers Squibb will supply investigational nivolumab. Only 100mg, 10mg/ml Nivolumab vials will be provided for this study. There are 5 vials per carton.

14.1.2 Toxicity:

Nivolumab is most commonly associated with immune-related adverse reactions. Most of these, including severe reactions, resolved following initiation of appropriate medical therapy or withdrawal of nivolumab.

Refer to investigator brochure for detailed toxicity information.

14.1.3 Formulation and preparation

Nivolumab Injection is a clear to opalescent, colorless to pale yellow liquid; light (few) particulates may be present. The drug product is a sterile, nonpyrogenic, single-use, isotonic aqueous solution formulated in sodium citrate, sodium chloride, mannitol, diethylenetriamine pentacetic acid (pentetic acid) and polysorbate 80 (Tween® 80), pH 6.0.

Abbreviated Title: Ph II Nivo IDH-mutant Gliomas

Version Date: 03/24/2023

Nivolumab injection can be infused undiluted (10 mg/mL) or diluted with 0.9% Sodium Chloride Injection, USP or 5% Dextrose, USP to concentrations no less than 1 mg/mL.

14.1.4 Stability and Storage

Store intact vials at 2°C to 8°C (36°F to 46°F); do not freeze. Protect from light. Do not shake. Shelf-life surveillance of the intact vials is ongoing.

Store the prepared infusion solution at room temperature or refrigerated. Do not freeze solutions prepared for infusion. Refer to investigator brochure for detailed stability information.

14.1.5 Administration procedures

Intravenous infusion 30 to 60 minutes. Do not administer as an IV push or bolus injection.

Administer through a 0.2 micron to 1.2-micron pore size, low-protein binding in-line filter.

16 APPENDICES

16.1 APPENDIX A: PERFORMANCE STATUS CRITERIA

Karnofsky Performance Scale	
Percent	Description
100	Normal, no complaints, no evidence of disease.
90	Able to carry on normal activity; minor signs or symptoms of disease.
80	Normal activity with effort; some signs or symptoms of disease.
70	Cares for self, unable to carry on normal activity or to do active work.
60	Requires occasional assistance but is able to care for most of his/her needs.
50	Requires considerable assistance and frequent medical care.
40	Disabled, requires special care and assistance.
30	Severely disabled, hospitalization indicated. Death not imminent.
20	Very sick, hospitalization indicated. Death not imminent.
10	Moribund, fatal processes progressing rapidly.
0	Dead.

16.2 APPENDIX B: NEUROLOGIC EVALUATION

0= No neurologic symptoms, fully active at home/work without assistance

Abbreviated Title: *Ph II Nivo IDH-mutant Gliomas*

Version Date: 03/24/2023

1= Minor neurologic symptoms, fully active at home/work without assistance

2= Moderate neurologic symptoms, fully active at home/work but requires assistance

[figure not shown]
3= Moderate neurologic symptoms, less than fully active at home/work and requires assistance

4= Severe neurologic symptoms, totally inactive requiring complete assistance at home or institution, unable to work

16.3 APPENDIX C: MANAGEMENT ALGORITHMS FOR ENDOCRINOPATHY, GASTROINTESTINAL, HEPATIC, NEUROLOGICAL, PULMONARY, RENAL, AND SKIN ADVERSE EVENTS

Endocrinopathy Management Algorithm

[figure not shown]
Rule out non-inflammatory causes. If non-inflammatory cause, treat accordingly and continue I-O therapy. Consider visual field testing, endocrinology consultation, and imaging.

Patients on IV steroids may be switched to an equivalent dose of oral corticosteroids (e.g. prednisone) at start of tapering or earlier, once sustained clinical improvement is observed. Lower bioavailability of oral corticosteroids should be taken into account when switching to the equivalent dose of oral corticosteroids.

GI Adverse Event Management Algorithm

[figure not shown]
Rule out non-inflammatory causes. If non-inflammatory cause is identified, treat accordingly and continue I-O therapy. Opiates/narcotics may mask symptoms of perforation. Infliximab should not be used in cases of perforation or sepsis.

Patients on IV steroids may be switched to an equivalent dose of oral corticosteroids (e.g. prednisone) at start of tapering or earlier, once sustained clinical improvement is observed. Lower bioavailability of oral corticosteroids should be taken into account when switching to the equivalent dose of oral corticosteroids.

Neurological Adverse Event Management Algorithm

[figure not shown]
Rule out non-inflammatory causes. If non-inflammatory cause, treat accordingly and continue I-O therapy.

Patients on IV steroids may be switched to an equivalent dose of oral corticosteroids (e.g. prednisone) at start of tapering or earlier, once sustained clinical improvement is observed. Lower bioavailability of oral corticosteroids should be taken into account when switching to the equivalent dose of oral corticosteroids.

Hepatic Adverse Event Management Algorithm

Rule out non-inflammatory causes. If non-inflammatory cause, treat accordingly and continue I-O therapy. Consider imaging for obstruction.

[figure not shown]
Patients on IV steroids may be switched to an equivalent dose of oral corticosteroids (e.g. prednisone) at start of tapering or earlier, once sustained clinical improvement is observed. Lower bioavailability of oral corticosteroids should be taken into account when switching to the equivalent dose of oral corticosteroids.

*I-O therapy may be delayed rather than discontinued if AST/ALT \leq 8 x ULN or T.bili \leq 5 x ULN.

**The recommended starting dose for grade 4 hepatitis is 2 mg/kg/day methylprednisolone IV.

Pulmonary Adverse Event Management Algorithm

[figure not shown]
Rule out non-inflammatory causes. If non-inflammatory cause, treat accordingly and continue I-O therapy. Evaluate with imaging and pulmonary consultation.

Patients on IV steroids may be switched to an equivalent dose of oral corticosteroids (e.g. prednisone) at start of tapering or earlier, once sustained clinical improvement is observed. Lower bioavailability of oral corticosteroids should be taken into account when switching to the equivalent dose of oral corticosteroids.

Renal Adverse Event Management Algorithm

[figure not shown]
Rule out non-inflammatory causes. If non-inflammatory cause, treat accordingly and continue I-O therapy

Patients on IV steroids may be switched to an equivalent dose of oral corticosteroids (e.g. prednisone) at start of tapering or earlier, once sustained clinical improvement is observed. Lower bioavailability of oral corticosteroids should be taken into account when switching to the equivalent dose of oral corticosteroids.

Skin Adverse Event Management Algorithm

Rule out non-inflammatory causes. If non-inflammatory cause, treat accordingly and continue I-O therapy.

Patients on IV steroids may be switched to an equivalent dose of oral corticosteroids (e.g. prednisone) at start of tapering or earlier, once sustained clinical improvement is observed. Lower bioavailability of oral corticosteroids should be taken into account when switching to the equivalent dose of oral corticosteroids.

*Refer to NCI CTCAE v4 for term-specific grading criteria.

^If SJS/TEN is suspected, withhold I-O therapy and refer patient for specialized care for assessment and treatment. If SJS or TEN is diagnosed, permanently discontinue I-O therapy.

[figure not shown]

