3.3 DOSE MODIFICATIONS

There are no planned dose reductions for nivolumab.

The tables below outline the criteria for delaying (then restarting) or stopping treatment by toxicity type.

Treatment will be discontinued if AE is not resolved for 4 weeks.

Skin Rash and Oral Lesions	Management
Grade 1	Continue treatment. No change in dose *.
Grade 2	Hold* until \leq Grade resolved. Consider steroid treatment $>$ 5-7 days Resume at same dose level.
Grade 3	Hold* until \leq Grade 1. Resume at same level at investigator discretion
Grade 4	Off protocol therapy
*Patients with purpuric or bullous lesions must be evaluated for vasculitis, Steven-Johnson syndrome, TEN, and autoimmune bullous disease including oral lesions of bullous pemphigus/pemphigoid. Pruritus may occur with or without skin rash and should be treated symptomatically if there is no associated liver or GI toxicity. Note skin rash typically occurs early and may be followed by additional events particularly during steroids tapering.	
Recommended management: See AE management guidelines (Appendix C)	

Liver Function AST/ALT/T. Bili *	Management
Grade 1	Continue treatment
Grade 2	Hold until less than or equal to Grade 1. Resume at same dose level. Consider steroid treatment if persists $>$ 5-7 days or worsens.

Liver Function AST/ALT/T. Bili *	Management
Grade 3	Off protocol therapy
Grade 4	Off protocol therapy
Continued treatment of active immune mediated hepatitis may exacerbate ongoing inflammation. Holding drug to evaluate LFT changes and early treatment are recommended. LFT changes may occur during steroid tapers from other events and may occur together with other GI events including cholecystitis/pancreatitis.	
Recommended management: See Hepatic AE management algorithm (Appendix C)	
* Total bilirubin not used for determining AEs in patients with Gilbert syndrome.	

Renal Function Serum Creatinine	Management
Grade 1	Continue treatment.
Grade 2	Hold until \leq Grade 1. Resume at same dose level.
Grade 3	Hold until \leq Grade 1. Resume at same dose level.
Grade 4	Off protocol therapy
For Grade 2 or greater, consider renal biopsy. Corticosteroids may be required for Grade 2/3, high dose for grade 4.	
Recommended management: see Renal AE management algorithm (Appendix C)	

Diarrhea/ Colitis	Management
Grade 1	Diarrhea/asymptomatic colitis, continue treatment at PI discretion.

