3.7.1 Criteria for Removal from Protocol Therapy

- Completion of protocol therapy
- Progressive disease (See [Appendix D](#) for treatment discontinuation guidance)
- Participant requests to be withdrawn from active therapy
- Unacceptable Toxicity as defined in Section [3.3](#)
- PI discretion
- Positive pregnancy test
- Patient becomes unable to tolerate an MRI study with intravenous gadolinium contrast.

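### The Section 3.3 liver table stops nivolumab at Grade 3 and 4, while the Appendix C hepatic footnote it leads to permits a delay, with no explicit rule on which prevails and an ambiguous 'or' between the footnote's limits

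*Combined protocol and SAP*

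**What the plan says.** Section 3.3 describes its own role: "The tables below outline the criteria for delaying (then restarting) or stopping treatment by toxicity type". In the liver table (AST/ALT/T. Bili), Grade 1 continues. Grade 2 is a delay: "Hold until less than or equal to Grade 1. Resume at same dose level". Grade 3 and Grade 4 each read "Off protocol therapy". The one carve-out is "Total bilirubin not used for determining AEs in patients with Gilbert syndrome". The table ends by naming the Appendix C hepatic algorithm as recommended management.

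In Appendix C (Section 16.3), a footnote to the hepatic algorithm states "I-O therapy may be delayed rather than discontinued if AST/ALT" is no more than 8 x ULN or total bilirubin is no more than 5 x ULN. The two limits are joined as "8 x ULN or T.bili". The next footnote concerns Grade 4 hepatitis.

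Section 3.7.1 lists among the reasons for removal "Unacceptable Toxicity as defined in Section" 3.3. Section 6.4 names CTCAE version 5.0 for adverse event reporting. Neither it nor any other section prints the AST/ALT or bilirubin grade limits.

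**The concern.** An investigator with a Grade 3 liver result finds a stop instruction in Section 3.3, follows that table's reference to Appendix C, and there finds permission to delay instead. The footnote matters only where the default is discontinuation, and in the liver table that default applies at Grades 3 and 4 alone. The two texts therefore seem to give different answers to the same question.

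At stake is whether a patient is re-exposed to nivolumab after a high-grade liver event, and whether two investigators with the same result would act alike. A second, separate difficulty is that the footnote does not say whether meeting one limit is enough, whether both must be met, or whether each limit applies only to its own test.

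**Working it through.** The plan states no figure on this point, so the check is a comparison of texts plus the logic of the footnote.

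**Step 1. Do the texts address the same decision?** In the liver table, by grade: 1 continue, 2 hold and resume, 3 and 4 off therapy. Discontinuation by grade occurs only at 3 and 4. The footnote offers delay in place of discontinuation, so it must qualify a stop instruction, and the neighbouring footnote shows that the algorithm reaches Grade 4. The flow chart is not in the text available for this review, so the box that carries the asterisk could not be checked. That the footnote bears on Grades 3 and 4 is an inference from its wording.

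**Step 2. What does the footnote allow?** Let A be AST/ALT ≤ 8 x ULN and B be total bilirubin ≤ 5 x ULN.

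| A | B | Delay if either suffices (literal 'or') | Delay if both are required |
|---|---|---|---|
| yes | yes | allowed | allowed |
| yes | no | allowed | not allowed |
| no | yes | allowed | not allowed |
| no | no | not allowed | not allowed |

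Delay is open in 3 of 4 combinations if either limit suffices and in 1 of 4 if both are needed. These are combinations of conditions, not proportions of patients. Examples under the literal reading, in multiples of ULN:

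- AST 15, bilirubin 1: allowed (B holds).
- AST 1, bilirubin 12: allowed (A holds).
- AST 7, bilirubin 6: allowed (A holds).
- AST 9, bilirubin 6: not allowed (neither holds).

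The last two show that the AST/ALT limit decides the outcome once bilirubin is above 5 x ULN. On a test-by-test reading, where each limit governs only elevations of its own test, the first two examples would not qualify.

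**Step 3. Where does the footnote overlap the stop rows of Section 3.3?**

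- *Literal 'or'.* Any Grade 3 or 4 AST/ALT with bilirubin ≤ 5 x ULN qualifies for delay. The overlap exists whatever the CTCAE cut-offs are.
- *Test by test.* Let g be the lower bound of Grade 3. The overlap is (g, 8] x ULN for AST/ALT, present only if g < 8, and (g, 5] x ULN for bilirubin, present only if g < 5. Because g is not in the documents, it was varied over 3, 4, 5, 6, 7, 8 and 10 x ULN as an assumption. AST/ALT overlaps for g from 3 to 7, and bilirubin for g of 3 or 4. At 8 and 10 there is no overlap for either.

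**Step 4. Is there a precedence rule?** Section 3.7.1 points to Section 3.3, and Section 3.3 points on to Appendix C. No sentence ranks the two. Elsewhere in Section 3.3, in the tables for all other events, high-grade exceptions are written out (for example lymphopenia, asymptomatic amylase or lipase, and electrolytes). None by multiple of ULN is written for the liver.

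**The case against.** The strongest reply is that Section 3.3 already governs. Its tables set the stopping criteria, Section 3.7.1 defines removal by them, and Appendix C is cited only as recommended management. This largely stands: a reader might infer that nothing indicates which text governs, and that goes too far. What is missing is an explicit statement. Section 3.3 itself sends the reader to the algorithm that carries the exception, and Section 4.1 relies on Appendix C algorithms to decide when corticosteroids are required, so the appendix is not mere background.

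It can also be said that the footnote is permissive, so a site that stops every Grade 3 or 4 event complies with both texts. That is true, but a site that uses the permission departs from Section 3.3, so the inconsistency remains. Section 3.3 also ends treatment when an adverse event is unresolved for 4 weeks. That rule limits how long a delay can last; it does not settle whether delay is open at Grade 3 or 4.

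Two stronger readings of the footnote are tempting. One is that its AST/ALT limit has no effect; the AST 7 and AST 9 examples with bilirubin 6 disprove this. The other is that the limits hardly restrict anything. That follows only from the literal 'or'. The test-by-test reading is equally available, and the flow chart that would show the footnote's scope cannot be seen here.

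**Conclusion.** The inconsistency stands and should be corrected. Section 3.3 stops Grade 3 and 4 liver elevations without a ULN-based exception, the Appendix C footnote permits delay within stated ULN limits, and no explicit rule ranks them. Under the literal 'or' the overlap does not depend on grade cut-offs. Under the test-by-test reading its extent depends on Grade 3 bounds that the documents do not give. Both conclusions assume that the footnote attaches to a discontinuation instruction at those grades, as its wording indicates.

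A reader might infer that the primary result is affected through who remains on drug at 6 months. The documents do not support this. Section 6.3.4 runs PFS to progression, and the study calendar keeps patients who stop early without progression on 8-weekly MRI until progression or 1 year from the start of treatment. Section 10.3.3 plans only frequency tables of event type and grade. No sample size, power or alpha figure changes. Nor can a number of affected patients be given, because the documents state no rate of high-grade liver events. The point concerns patient safety and consistent conduct.

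**What to change.** Reconcile the Section 3.3 liver table with the Appendix C footnote in an amendment. Either state in Section 3.3 that the appendix exception applies, and to which values, or state that Section 3.3 overrides it in this trial and remove the footnote. If the footnote stays, say whether one limit or both must be met, or whether each applies to its own test. Add one general sentence to Section 3.3 saying which text prevails wherever it and Appendix C differ. Which clinical rule to adopt is for the sponsor.

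The cost is a sentence or two in Section 3.3 and one edited footnote, with no added data or visits.
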